2.4 IMMUNE FACTORS

A major breakthrough in the understanding of sarcoidosis occurred with the application of the technique of bronchoalveolar lavage (BAL) (Crystal et al, 1981; Hunninghake and Crystal, 1981). Up until that time, sarcoidosis had been characterized as a disease of down regulated immunity, the hallmark being the anergy found in the disease (Daniele et al, 1980). Leukopenia and lymphopenia were often observed in the disease (Lower et al, 1988). With the introduction of BAL, it became clear that sarcoidosis was characterized by increased number and activation of T cells and other components of cell mediated immunity in the area of inflammation. These studies demonstrated that peripheral blood studies provided little insight into the inflammatory response of the disease and that BAL provided unique information about the inflammatory response of the lung during disease activity.

Spontaneous resolution of disease was associated with a normalization of the CD4+ T cell to CD8+ T cell ratio prior to a fall in the proportion of lymphocytes in the BAL (Ceuppens et al, 1984).

In patients treated with corticosteroids, clinical response was associated with a fall in the CD4+ T cell to CD8+ T cell ratio in the BAL samples (Baughman and Lower, 1990; Ceuppens et al, 1984).

2.5 CLINICAL COURSE

The natural course of sarcoidosis can be quite variable (James, 1994). Up to 80% of patients will have self-limiting disease with no long-term sequela. A percentage of patients will be left with fibrotic disease but no chronic active disease. A small percentage of patients will have chronic, longstanding disease. The percentage of patients who have chronic disease varies from population to population. It has also been well established that certain manifestations of the disease are more likely to be associated with prolonged, chronic disease (Neville et al, 1983). For example, patients with lupus pernio, the disfiguring facial lesions of sarcoidosis, are very likely to have chronic and, perhaps, lifetime disease. Those patients with erythema nodosum and hilar adenopathy, on the other hand, have a better than 90% chance of resolution of the disease within two years and no evidence of recurrence in their lifetime. The two-year outcomes can be helpful to define categories of disease which may be related to etiology.

It has been suggested that patients with different ethnic backgrounds will have different outcomes. In sarcoidosis clinics in the United States, the percentage of patients with chronic disease is over thirty percent (Baughman et al, 1987; Johns et al, 1974). These clinics are often composed of predominantly African-American inner city patients. It is not clear whether the high percentage of chronic disease results from a selection bias on the basis of the investigator's interest in sarcoidosis or from the condition's natural history. There has been one report of a clinic in London in which chronic disease was seen in different frequencies depending on the patient's underlying ethnicity, with chronic disease seen much more frequently in West Indians than in Irish descendants (Honeybourne, 1980).

There are several ways that socioeconomic status may influence outcome of the disease. These include access to medical care, attitudes towards therapy, and social support. One advantage of this multicenter study is that cases will have a wide variety of social and economic backgrounds so that the influence of these characteristics on disease presentation and two-year outcome can be examined.

2.6 CONCLUSIONS

The proposed multicenter, case control study will provide information essential to the ultimate determination of the cause(s) of sarcoidosis. The additional prospective study of clinical course will help to establish a broader perspective of the outcome of sarcoidosis patients.

CHAPTER 3

OBJECTIVES AND RESEARCH QUESTIONS

3.1 INTRODUCTION

The goals of ACCESS are to collect and analyze data and biologic specimens to address the hypotheses that (1) sarcoidosis occurs in genetically susceptible individuals through (2) alterations in immune response and/or (3) following exposure to environmental, occupational and/or infectious agents and that (4) genetic, environmental and socioeconomic factors affect initial pattern of organ involvement and clinical course (disease severity) over two years. Specific hypotheses to be addressed in the case control study are that genetic factors, infectious, occupational or environmental factors and immune alterations affect risk for sarcoidosis. Objectives of the study of two-year outcome among 240 cases include evaluation of the association of initial category of involvement with category of involvement 24-30 months later; evaluation of clinical presentation, radiographic abnormalities, pulmonary function test results and ancillary data as prognostic indicators; description of indications for therapy; evaluation of outcomes of therapy; and evaluation of the relationship among specific environmental, genetic and socioeconomic factors with the two-year outcome (morbidity and mortality).

A central repository is established to store DNA and plasma specimens for later testing of hypotheses concerning genetic, environmental and occupational factors and infectious agents in the etiology of sarcoidosis. DNA specimens for the repository are prepared in a DNA Core Laboratory according to standardized procedures.

The ACCESS Principal Investigators met in June 1996 to review mini-applications submitted for special laboratory studies. They assigned priorities to the approved studies. Mini-applications submitted and funded are listed in Section 3.6.

3.2 GENETIC FACTORS

Using a case control study design, we will quantify familial aggregation and define risk of sarcoidosis among different classes of relatives. Family history regarding sarcoidosis is obtained from each case and matched control and familial aggregation measured. Affected first degree relatives, who are age 18 years or older and who agree to participate, are interviewed by telephone and their medical records reviewed.

3.3 INFECTIOUS, OCCUPATIONAL AND ENVIRONMENTAL FACTORS

An interviewer-administered occupational / environmental questionnaire is used to obtain information to address the following hypotheses:

- Sarcoidosis patients (cases) are more likely to report employment in particular occupations or occupational categories when compared with a non-sarcoidosis referent group (controls). The categories considered include:
 - A. Employment in metal dust and metal fume associated industries.
 - B. Employment as health care workers.
 - C. Employment as child care providers and educators.
 - D. Employment as firefighters.
 - E. Employment in the military.
 - F. Employment in agriculture.
 - G. Occupational exposure to organic dusts.
 - H. Employment in mechanically ventilated buildings.
 - I. Employment in environments where exposure to microbial bioaerosols occurs.
 - J. Occupational exposure to chemicals that can produce hypersensitivity pneumonitis or granulomatous lung disease (e.g., isocyanates, pyrethrums).
 - K. Employment indoors.
 - L. Employment in dusty trades.

- M. Frequent close contact with co-workers or others during the work day.
- 2. Sarcoidosis patients (cases) are more likely to report particular environmental exposures when compared with a non-sarcoidosis referent group (controls). The exposures considered include:
 - A. Avocational exposure to metal dust and fumes (e.g., welding, jewelry making).
 - B. Avocational exposure to children.
 - C. Exposure to microbial contamination and bioaerosols in the home environment.
 - D. Exposure to organic dusts in a home environment.
 - E. Tobacco exposure.
 - F. Prior use of medications known to produce hypersensitivity lung diseases or granulomatous disease in other organs.
 - G. Rural residence.
 - H. Exposure to animal (including bird) antigens.

As part of the occupational and environmental questionnaire, antecedent occupational histories are recorded. Case and control occupations and industries are coded using standardized industrial codes (SIC) and standardized occupational codes (SOC) to test the following hypotheses:

 Sarcoidosis patients (cases) are more likely to have been employed in certain occupational categories or industries when compared with a non-sarcoidosis referent group (controls).

Specifically, we propose to test the hypothesis that occupational categories sharing common chemical or biological material exposures confer similar risks of sarcoidosis.

2. Sarcoidosis patients (cases) are more likely to report employment in particular occupations or occupational categories immediately prior to diagnosis of their sarcoidosis conditions when compared to non-sarcoidosis referent group (controls).

3. Sarcoidosis patients (cases) are more likely to have a "dose-related" risk associated with their employment in particular occupational/industrial categories when compared with non-sarcoidosis referent group (controls), based on duration of employment.

Determination of whether or not there is an increased frequency in cases as compared to controls of history of exposures to infectious agents is an important objective of ACCESS. Sarcoidosis may represent a granulomatous response initiated by an environmental, occupational and/or infectious agent.

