1.1 INTRODUCTION

A Case Control Etiologic Study of Sarcoidosis (ACCESS) is a multicenter study sponsored by the National Heart, Lung and Blood Institute (NHLBI). The study is a case control study to investigate the etiology of sarcoidosis. The primary investigation is the study of etiology in which 720 patients with sarcoidosis representing both men and women, white and minority race/ethnicity and the spectrum of disease severity will be enrolled as will 720 age, gender and race/ethnicity matched controls recruited through random digit dialing to represent the general population. A prospective cohort study of the first 240 cases enrolled in the case control study will be used to define categories of outcome that may be related to the etiology of sarcoidosis and to describe the clinical course of sarcoidosis.

Sarcoidosis is a systemic granulomatous disease of unknown etiology. The organ systems most frequently of concern in sarcoidosis are the respiratory system (especially the lower respiratory tract, but also the large airways and upper respiratory tract), the eyes and the skin; involvement of the liver, nervous system, kidneys and the musculoskeletal system may be found. Sarcoid inflammation in vital organs (e.g., lungs, heart or nervous system) can be fatal, but for most patients the clinical course is benign.

Ten clinical centers, located at major medical centers/hospitals in the United States, are responsible for screening and recruitment of eligible sarcoidosis cases and matched controls. The ACCESS Clinical Coordinating Center is responsible for the study's statistical design, data collection and management, and analysis of study results. The Project Office, located in the Lung Biology and Disease Program of the Division of Lung Diseases at the NHLBI, is responsible for the overall direction and administration of ACCESS in collaboration with the Study Chairman, who was appointed by the NHLBI Director. A central repository for storage of case and control specimens is operated by McKesson Bioservices under a contract with the NHLBI. Specialized Core Laboratories also participate in the study.

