Epidemiologic studies do provide several clues regarding an infectious or environmental agent for sarcoidosis. Manifestations of the disease can be seasonal (Bardinas et al, 1989; Henke et al, 1986; James, 1961; Putkonen et al, 1966; Selroos, 1969). The incidence of sarcoidosis is higher in health care workers than in the general population. Clusters of cases also imply infectious or environmental etiologies. A well documented clustering occurred on the Isle of Man, an area of Great Britain with a cloistered population (Hills et al, 1987; Parkes et al, 1985; Parkes et al, 1987). The most impressive finding in that study was a higher likelihood of contact with an individual with sarcoidosis among cases (39.6%) compared to controls (1.1%).

The lungs and skin -- two common target organs for sarcoidosis -- are regularly in contact with environmental antigens. Occupational and environmental exposures include many potential antigens that can induce sensitization -- a cell-mediated immune response responsible for the development of granulomas (Boros, 1988; Semenzato et al, 1985). Occupational and environmental factors cause a variety of granulomatous diseases that resemble sarcoidosis, including: chronic beryllium disease due to inhalation and sensitization by beryllium oxide, and other metal-induced granulomatous lung diseases (aluminum, titanium, zirconium); hypersensitivity pneumonitis due to both organic and inorganic antigens; tuberculosis and atypical mycobacterial infection; and fungal infections.

There is a marked predilection for disease to develop in early adulthood (age specific clustering), with the disease notably rare in children and early teens (Gordis, 1973; Pattishall et al, 1986) and rare in the elderly beyond age 70 (Cooch, 1961). This observation might suggest that exposure to the etiologic agent(s), whether they are antigenic or infectious, may first occur about the time that individuals reach working age, raising speculation about the contribution of occupational exposures.

Although studies vary in their findings with regard to the male:female ratios of sarcoidosis, most suggest a slightly higher rate in women. In the only population-based incidence study of sarcoidosis in the United States (Henke et al, 1986), however, similar age-adjusted incidences were

found in the two genders (5.9/100,000 person/years for men and 6.3/100,000 person-years for women).

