6.2 CASE SELECTION

It is planned that the total study population will consist of 720 cases and 720 controls. Each Clinical Center enrolls, interviews, examines and collects blood specimens from 72 cases with sarcoidosis and enrolls, interviews and collects blood specimens from 72 matched controls during the recruitment period (November 1, 1996 through June 30, 1999).

Cases may be recruited from a variety of clinical settings, including inpatient, hospital-based outpatient, and non hospital-based outpatient. Each Principal Investigator defines, in advance, the geographic area from which the center recruits patients for the study. Permission to contact patients identified in a clinical setting must be obtained initially from the attending physician of record, in advance of study enrollment. Potential cases are informed that a payment will be given to reimburse them for parking costs, meals and other expenses (including lost time from work) at the medical center, and transportation costs.

At the time of enrollment into the study, patients are categorized according to their clinical condition at the time of initial diagnosis, i.e., the day of biopsy confirmation. Table 6-2A outlines the disease categories that were used to describe cases beginning November 1996. An additional revised classification system was used beginning September 1997 and is given in Table 6-2B. The purpose of revising the disease categories is to encourage use of information on facets of the clinical presentation of sarcoidosis that were not readily appreciated in the hierarchical, initial classification of disease categories. This information is used in ACCESS to assess the spectrum of clinical sarcoidosis presentations represented among the ACCESS cases.

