6.3.1 Random Digit Dialing Controls

Cases are matched in a one to one ratio to controls selected through random digit dialing. Random digit dialing facilitates the selection of a control group that approximates a probability sample in the population. Random digit dialing (RDD) is used to identify potential controls through an unbiased clustered random sample of households with telephones (Waksberg, 1978). Cluster sampling of telephone households and a stratified sample of age-, gender-, and self-identified racematched individuals are used (Hartge et al, 1984).

The groups selected to generate telephone numbers, Survey Sampling Inc. (SSI), and to perform the telephone recruitment of potential controls, Telesurveys Research Associates (Random Digit Dialing (RDD) Interview Group), work under the direction of the Clinical Coordinating Center. The RDD callers are responsible for making initial telephone contact with potential controls in the geographic areas of the Clinical Centers.

Once the RDD Interview Group recruiter has established the eligibility, availability and willingness of the potential control to participate, the potential control is informed that an interviewer from the Clinical Center will be in touch soon to set up an appointment to meet for questionnaire

administration and phlebotomy. Potential controls are informed that a payment will be given to them after they complete the study interview to reimburse them for parking costs, meals and other expenses (including lost time from work) at the medical center, and transportation costs.

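### Employees of the recruiting medical centers may be found as cases more readily than other residents, which would bias the health-care-worker odds ratio upward; the protocol has no check for this

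*Protocol*

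**What the plan says.** **Hypothesis.** Protocol section 3.3, hypothesis 1, item B is "Employment as health care workers". The same section plans analyses by industry and occupation codes (SIC and SOC), by employment just before diagnosis, and by duration of employment, so health-care work enters several times. Section 2.3 already expects a positive answer: "The incidence of sarcoidosis is higher in health care workers than in the general population".

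**Cases.** Section 1.1: "Ten clinical centers, located at major medical centers/hospitals in the United States, are responsible for screening and recruitment of eligible sarcoidosis cases". Section 6.2: "Cases may be recruited from a variety of clinical settings, including inpatient, hospital-based outpatient, and non hospital-based outpatient". Section 6.2 adds: "Each Principal Investigator defines, in advance, the geographic area from which the center recruits patients for the study".

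**Controls.** Section 6.3.1 describes "an unbiased clustered random sample of households with telephones" and states: "Random digit dialing facilitates the selection of a control group that approximates a probability sample in the population". Section 4.2.2 places the dialing in the case's local community, and section 7.2 in the same telephone exchange. Section 6.3 matches on age, gender and race only.

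**Safeguards.** Exclusions in sections 1.4 and 6.4 concern medical history, age, competence to consent and likely compliance. Nothing flags, matches on or separately analyzes employees of the recruiting centers. Section 12.1 nevertheless asserts that bias and confounding will be adequately controlled. Section 12.3.2.2 relies on matching and conditional logistic regression.

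**The concern.** A case enters the study by reaching a clinic linked to one of ten medical centers. A control enters by answering a household telephone. For most exposures in section 3.3 that difference has no obvious link to the exposure. For health-care employment it does, because the recruiting institution employs people who count as exposed. If staff with sarcoidosis are more likely than other residents to be diagnosed at, referred to or recruited by their own center, the probability of becoming a case depends on the exposure being tested.

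Matching on age, gender and race does not address this. Drawing controls from the case's neighborhood aligns geography, not employer. Conditional logistic regression adjusts for measured covariates, but it cannot undo selection on the exposure itself.

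At stake is the reading of hypothesis 1B and of the health-care entries in the job-code and duration analyses. Because section 2.3 reports earlier findings in the same direction, an artefact would look like replication and would lend support to an infectious or occupational cause. Case screening logs could offer little help: by section 6.2 they held demographics, health care coverage and reasons for ineligibility or refusal, and they were stopped in October 1997, during recruitment.

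**Working it through.** **Inputs from the protocol.** 720 pairs, one control per case, two-sided alpha 0.05 (sections 12.2.1 and 6.2).

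**Inputs that are assumptions.** The documents give none of these:
- p, health care workers among controls: 5% to 10%
- f, share of local health care workers employed at the recruiting center: 5% to 20%
- r, chance that an employee with sarcoidosis becomes a case, relative to another resident with sarcoidosis: 1 to 5

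**Step 1: reproduce the protocol's power figure.** Section 12.2.1 with one control per case is power = Φ(|p1 − p0|·√(N/ψ) − 1.96). At correlation 0, ψ = p1 + p0 − 2·p1·p0. For p0 = 0.05 and odds ratio 2.0:
- p1 = 0.10/1.05 = 0.0952
- difference = 0.0452
- ψ = 0.1357
- power = Φ(0.0452 × √(720/0.1357) − 1.96) = 0.909

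Table 2 prints 0.909. No stated figure is in dispute.

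**Step 2: apparent odds ratio with no true effect.** Controls are sampled at the population rate, so their odds of being a health care worker are p/(1 − p). Among cases the health care workers carry weight (1 − f) for non-employees and f·r for employees, so the odds are p[(1 − f) + f·r]/(1 − p). The ratio is

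apparent OR = (1 − f) + f·r = 1 + f(r − 1).

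**Step 3: numbers.** The last column is the chance of a significant positive result at correlation 0, for p = 5% and p = 10%. The nominal value is 2.5%.

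| f | r | apparent OR | false positive |
|---|---|---|---|
| any | 1 | 1.00 | 2.5% |
| 5% | 2 | 1 + 0.05 × 1 = 1.05 | 4.0% to 4.7% |
| 10% | 3 | 1 + 0.10 × 2 = 1.20 | 12% to 19% |
| 10% | 5 | 1 + 0.10 × 4 = 1.40 | 32% to 53% |
| 20% | 5 | 1 + 0.20 × 4 = 1.80 | 78% to 96% |

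The rows for 1.00, 1.20, 1.40 and 1.80 can be read directly from the protocol's Table 2, in the columns for 0.05 and 0.1 of controls exposed.

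**Step 4: the same thing in case counts.** Suppose an excess of 1% of cases, 0.01 × 720 ≈ 7 people, are health care workers from the centers, with p0 = 5%. Then p1 = 0.01 + 0.99 × 0.05 = 0.0595, the odds ratio is (0.0595/0.9405)/(0.05/0.95) = 1.20, and rejection is about 12%. By the formula in step 2 this needs r = 3 at f = 10%. The excess is put in here, not derived.

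**Step 5: what restriction does.** With center employees removed from both groups, the odds are p(1 − f)/(1 − p) in cases and in controls. The ratio is 1 whatever r is.

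**The case against.** The strongest reply is that clinic cases with population controls are not biased by that fact alone. Bias needs r above 1, and nothing in the protocol says that center staff are diagnosed or recruited preferentially. With r = 1 the apparent odds ratio is exactly 1.00. This stands: the inflation is a conditional risk.

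Several features also limit the problem. Cases come from non hospital-based settings too, within a catchment fixed in advance; section 6.2 asks for efforts to enroll every patient from each source; and controls come from the case's locality. Center staff in jobs that are not health-care jobs would enter as unexposed cases and pull the other way. These points stand as reasons to expect a smaller effect. They do not remove the dependence of case entry on employer.

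A further reply is that an extra analysis belongs in a statistical analysis plan, and that section 3.7 calls the study hypothesis-generating. The first is only partly met: which models are run could wait, but whether employer is known depends on what is collected during recruitment. The second lowers the stakes but does not dispose of the point, since a spurious lead that agrees with earlier reports is hard to dislodge.

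A reader might go further and infer that center employees can appear only on the case side. The documents contradict that. No exclusion in sections 1.4 or 6.4 bars an employee, and one living in the case's community can be dialed and enrolled as a control.

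**Conclusion.** The point holds as a conditional one. Case ascertainment runs through workplaces that are themselves exposed under hypothesis 1B, control ascertainment does not, and the protocol has no step that would detect or limit the resulting bias. If center employees with sarcoidosis are ascertained preferentially, the health-care-worker odds ratio is too high, and the analysis in section 12.3.2.2 would not correct it.

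The size is unknown. Under the assumed ranges it runs from nothing (r = 1), through small (1.05), to an odds ratio that could be taken for a modest etiologic effect (1.20 to 1.40). The value 1.80 needs both f = 20% and r = 5. All of these treat employees as reachable controls at their population rate, count only employees in health-care jobs, and take case and control exposures as uncorrelated.

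The documents do not support the conclusion that the odds ratio is inflated, only that it would be under unequal ascertainment, which they neither state nor rule out. The weakness lies in how sections 6.2 and 6.3 combine for this exposure, not in the hypothesis itself. It warrants an inexpensive safeguard, not a change of design.

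**What to change.** 1. From the occupational history, identify every case and control employed by a recruiting Clinical Center or its affiliate at the diagnosis date or, for controls, the reference date. Section 3.3 mentions coded occupation and industry but not employer, so first confirm that employer is captured and add an item if it is not.
2. State in section 12.3.2.2 that hypothesis 1B and the health-care codes in the SIC/SOC and duration analyses are also run on pairs with neither member flagged, and reported beside the all-pairs result. The same rule applies to cases and controls.
3. State that a positive all-pairs result will not be interpreted as etiologic unless it persists in the restricted analysis.

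**Cost.** One variable, one further model per analysis, and somewhat lower precision in the restricted set. As an illustration with p = 5%, f = 10%, r = 3, flagged health care workers would number about 720 × 0.005 ≈ 4 controls and 720 × 0.015/1.01 ≈ 11 cases, so roughly 14 of 720 pairs would drop out. Flagged staff in other jobs would add to that. If employer was not recorded for pairs already enrolled, it would have to be recovered or those pairs reported as unclassified.
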